# V. Descriptive analyses

- a. Calculate frequencies of the version of the protocol participants were enrolled.
- b. Characterize baseline cohort overall and by randomization arm for demographic, clinical, and patient characteristics in a table with 5 columns (overall, placebo, either INI, HDINI, LDINI) using descriptive statistics based on the variable in question (e.g., means and standard deviations, median and interquartile range, and percentages).
  - i. These characteristics will be included: age, sex, race, ethnicity, years of education, ADI (if possible), disease subtype (relapsing remitting MS vs. progressive MS), body mass index (BMI), disease duration, MS disease modifying therapy (DMT; categorized as injectable, oral, infusion/monoclonal ab), number of relapses in the past year, EDSS score, anti-depressant, stimulant use, total number of symptomatic therapies, DXA scan results (total body mass, total fat mass, total lean mass, visceral fat mass, body fat%), version of protocol enrolled under, fasting insulin, fasting glucose, HOMA-IR.
- c. Characterize SDMT scores overall and by randomization arm at baseline and over time. Two versions of this analysis will be created: 1) including baseline, and weeks, 6, 12 and 24, 2) including baseline and weeks 6, 12, 24, 36 and 48.
  - i. Characterize missing data in SDMT by randomization arm and by time
  - ii. Calculate descriptive statistics for SDMT levels by randomization arms and by time.
  - iii. Plot means (SD) of SDMT levels by randomization arm over time
  - iv. Create spaghetti plots with overlaid loess curves for SDMT by randomization arm over time.
  - v. Plot SDMT by month of study enrollment and by randomization arm and time to confirm no differences in allocation by calendar time.

## VI. Outline of protocol changes

Outline of timing of protocol changes by calendar time.

## VII. Consort diagram

a. A consort diagram will be created with the following levels: assessed for eligibility, randomized, treatment allocation, follow-up and analytic cohort.

## VIII. Regression models: Modified intention to treat analyses

- a. Analyses will adjust for age, sex, and years of education. We will also incorporate variables with differences between the treatment arms that exceed 10% as identified using results of the descriptive analyses.
- b. For analytic models for each outcome, the primary hypothesis test will compare INI (regardless of dose) versus PLAC and will be conducted first. Secondary pairwise tests comparing LDINI versus PLAC, HDINI versus PLAC, HDINI will then be conducted.
- c. Analyses will first be conducted first through the week 24 measure (0, 6, 12, 24). Secondary analyses will include weeks 36 and 48 (0, 6, 12, 24, 36, 48) to evaluate a potential sustained effect post cessation of treatment.
  - i. The week 24 visit must have occurred within 25 weeks (i.e., the protocol outlines a 1 week visit window).
- d. Eligible participants for the primary analysis are those with baseline or screening SDMT data
- e. Missing values for key baseline covariates of interest is expected to be small; however, primary analyses will include a missing indicator level for the categorical variable if it is included in analytic models.

- f. For mixed effects models, time will be considered as a linear variable in primary analyses.
  - i. Sensitivity analyses will evaluate potential non-linearity in changes over time using appropriate methods (e.g., quadratic terms for time or splines).
- g. Primary outcome: change in SDMT using raw scores over time
  - i. Change in the raw SDMT score over time will be assessed using a linear mixed effects model with unstructured covariance structure, random intercepts. If model fit is improved with the addition of random slopes, they will be added. The term of interest will be the coefficient for the cross-product term between INI and time.
- h. Secondary outcomes
  - i. Adverse events
  - ii. Change from baseline cognitive function in the tests listed below.
    - Rate of change in each cognitive test will be assessed using a linear mixed effects model with unstructured covariance structure, random intercepts. If model fit is improved with the addition of random slopes, they will be added. The term of interest will be the coefficient for the cross-product term between INI and time.
  - iii. Change in multiple sclerosis (MS) functional composite (MSFC)
    - 1. Rate of change in MSFC Z scores (and component Z scores) using a linear mixed effects model with unstructured covariance structure, random intercepts. If model fit is improved with the addition of random slopes, they will be added. The term of interest will be the coefficient for the cross-product term between INI and time.
    - 2. Rate of change in raw components using a linear mixed effects model with unstructured covariance structure, random intercepts. If model fit is improved with the addition of random slopes, they will be added. The term of interest will be the coefficient for the cross-product term between INI and time. A log transformation will be applied in if data are skewed based on visual inspection.
    - 3. For 20% change models, we will fit statistical models if ≥10 events occurred. Time to 20% worsening in MSFC (and components) using a Cox proportional hazards model.
    - 4. Plot unadjusted results using Kaplan Meier curves for time to event outcomes and test for significance using log-rank test (or other appropriate test if assumptions are not met for log-rank).
  - iv. Change in health-related quality of life using the functional assessment in MS (FAMS) score.
    - Rate of change in quality of life using a linear mixed effects model with unstructured covariance structure, random intercepts. If model fit is improved with the addition of random slopes, they will be added. The term of interest will be the coefficient for the cross-product term between INI and time.
    - For ≥1 SD improvement, we will fit statistical models if ≥10 events occurred. Time to ≥1 SD improvement in FAMS total score and subscale scores will be assessed via Cox proportional hazards model.
    - 3. Plot unadjusted results using Kaplan Meier curves and test for significance using log-rank test (or other appropriate test if assumptions are not met for log-rank).
  - v. Change in sleep quality
    - Rate of change in global sleep quality using PSQI using a linear mixed effects model with unstructured covariance structure, random intercepts. If model fit is improved with the addition of random slopes, they will be added. The term of interest will be the coefficient for the cross-product term between INI and time.
  - vi. Change in depression using Beck Depression Inventory-II
    - 1. Rate of change in total depression using a linear mixed effects model with unstructured covariance structure, random intercepts. If model fit is improved with the addition of random slopes, they will be added. The term of interest will be the coefficient for the cross-product term between INI and time.

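### SAP VIII.a adds covariates by an undefined 10% imbalance rule: negligible for the primary SDMT test, but able to overload the secondary Cox models, which may be fitted from 10 events

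*SAP*

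**What the plan says.** SAP section VIII opens with a covariate rule for its analyses. The fixed part is "Analyses will adjust for age, sex, and years of education". The open part is "We will also incorporate variables with differences between the treatment arms that exceed 10% as identified using results of the descriptive analyses". The descriptive analyses are those of section V.b, whose table has separate columns for placebo, either insulin dose, high dose and low dose.

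For the primary outcome (VIII.g.i), "The term of interest will be the coefficient for the cross-product term between INI and time". The same section holds the Cox models: "Time to 20% worsening in MSFC (and components) using a Cox proportional hazards model", and the one-SD "improvement in FAMS total score and subscale scores will be assessed via Cox proportional hazards model". The event threshold is 10: "For 20% change models, we will fit statistical models if ≥10 events occurred", with the same threshold for FAMS. For these outcomes the SAP also plans unadjusted Kaplan-Meier curves with a log-rank test (VIII.h.iii.4 and VIII.h.iv.3).

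On the population, VIII.d says "Eligible participants for the primary analysis are those with baseline or screening SDMT data". On missing covariates, VIII.e expects few and adds that "primary analyses will include a missing indicator level for the categorical variable if it is included in analytic models".

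The protocol (Study Treatment) stratifies randomisation by relapsing versus progressive MS. In the SAP, subtype is a baseline-table row (V.b.i) and a subgroup variable (IX.b.iv), not a fixed covariate.

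**The concern.** The rule leaves the metric open (percentage points, relative difference in means or standardised difference) and also the contrast (pooled insulin versus placebo, or any pair of arms). In a randomised trial baseline differences between arms arise by chance, so the rule lets chance choose the model, and different readings choose different models. Two consequences follow.

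- **Cox models.** VIII.a is not limited to the mixed models, and only the Kaplan-Meier and log-rank results are labelled unadjusted. Up to 10 Cox models are therefore exposed: MSFC and three components, FAMS total and five subscales. Many covariates on 10 events make the insulin hazard ratio unreliable.
- **Who is analysed.** VIII.e deals with missing values only for categorical covariates. If the rule brings in a numeric covariate and software deletes incomplete records, participants eligible under VIII.d are lost.

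The rule also tends to pass over subtype, because stratified randomisation balances it.

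**Working it through.** **Inputs.** 35 per group, 105 in total (Protocol, Sample Size and Power), so pooled insulin versus placebo is 70 versus 35. V.b.i lists 24 characteristics, counting five DXA measures; removing the three fixed ones leaves 21 candidates (7 categorical, 14 numeric). The plan gives no figure for the rule itself. Its power statement, used only to confirm the inputs, reproduces: 6/(9 × √(2/35)) = 2.79; 2.79 − 1.96 = 0.83; power 0.796, against 80% stated.

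**Step 1: how often chance trips the rule, with no true imbalance.** Let s = √(1/70 + 1/35) = 0.207.

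- Standardised difference above 0.1, pooled: P(|Z| > 0.1/0.207 = 0.483) = 0.63. Any pair of three arms, simulated: 0.91.
- Relative difference in means above 10%, pooled: P(|Z| > 0.1/(CV × 0.207)). This is about 0 at CV 0.1, 0.33 at CV 0.5 and 0.63 at CV 1.0 (any pair: 0.68 at CV 0.5, 0.91 at CV 1.0).
- Binary covariate, more than 10 percentage points, exact binomial:

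| Prevalence | 0.05 | 0.10 | 0.20 | 0.35 | 0.50 |
|---|---|---|---|---|---|
| Pooled insulin vs placebo | 2% | 8% | 20% | 28% | 30% |
| Any pair of arms | 12% | 33% | 54% | 65% | 68% |

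If the standardised reading applied to all 21 candidates, the expected number added is 21 × 0.63 = 13 (pooled) or 21 × 0.91 = 19 (any pair). A simulation of the V.b.i mix, with assumed category levels, CVs and correlations, added on average 5.5 variables (points/relative, pooled), 10.3 (points/relative, any pair), 13.0 (standardised, pooled) or 18.4 (standardised, any pair). Subtype entered in 0-4% of trials (assumed blocks of 3, 6 or 9).

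**Step 2: primary SDMT test.** A baseline main effect is constant over time. With complete data it cannot explain within-person change, so it does not move the insulin-by-time coefficient. Simulation (visits 0, 6, 12, 24; SD 9; assumed correlation 0.5) gave a shift of 0.00 points with complete data and 0.06-0.12 with 17% dropout. Type I error was 5.7-6.0%, against 5.9% with the three fixed covariates (simulation SE 0.6%).

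**Step 3: Cox models at the 10-event threshold.** Events per parameter: 10/4 = 2.5 with insulin and the fixed three; 10/16 = 0.6 with 12 more.

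Simple null simulation (105 participants, 70 vs 35, independent normal covariates):

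- Likelihood-ratio rejection was about 5% with up to 4 covariates, 5-9% with 7 or 8 (runs differ), and 8-13% with 12-16. Wald rejection was at or below about 5%.
- The SD of the log hazard ratio was 0.73 with 3 covariates, 1.05 with 12 and 1.56 with 17. Estimated hazard ratios below 0.2 or above 5 made up 4%, 13% and 22%.
- At 20 events, likelihood-ratio rejection was up to about 9% with 12-16 covariates.
- The unadjusted log-rank test rejected in 3-4% at 10 events and 3-6% at 20.

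A more detailed simulation applied the rule to the correlated V.b.i mix, across the four readings:

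| | Closed list (fixed three plus subtype) | With the rule |
|---|---|---|
| 10 events, likelihood ratio | 5-6% | 8-20% |
| 10 events, Wald | 2-3% | 3-6% |
| 10 events, hazard ratio not estimable | 1% | 1-70% |
| 20 events, likelihood ratio | 6% | 6-16% |
| 20 events, Wald | 4-5% | 5-13% |

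The upper ends come from the standardised readings.

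**Step 4: missing numeric covariates.** Take three sources (ADI, DXA, fasting labs), each missing independently at an assumed rate m, with listwise deletion. If one source enters, 105(1 − m) remain: 103, 100 or 94 at m = 2%, 5% or 10%. If all three enter, 105(1 − m)³ remain: 99, 90 or 77. Simulated shifts in the 24-week SDMT contrast ran from 0.2-0.4 points (2%) to 0.5-1.1 (10%). All are below one standard error (1.78 with all participants).

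**The case against.** **The primary test is barely touched.** This stands. A reader might infer that the rule undermines the SDMT result or that omitting subtype costs power. The documents do not support either: the tested term is insulin by time, and no precision gain from subtype is claimed.

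**The same event outcomes have an unadjusted log-rank test.** This also stands, and it limits the damage to the Cox hazard ratios and their tests.

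**The 8-20% range is a worst case.** Largely fair. It is a likelihood-ratio figure at the minimum event count, and the SAP names no Cox test. It is highest where many fits are not estimable; in one run with 16 covariates, dropping such fits lowered rejection from 12.8% to 10.3%. How often an outcome would have so few events is unknown.

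**Missingness may be trivial.** VIII.e expects little, and DXA and fasting labs are scheduled for everyone at baseline. The rates above and listwise deletion are assumptions. The shifts show no established bias or type I error effect.

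**The rule is pre-specified and uses baseline data only.** True. A reader might infer that an unblinded statistician could choose the favourable reading, or that covariates could enter with time interactions. The protocol does leave the statistician unblinded, but nothing suggests misuse. The SAP names only the insulin-by-time product, so main effects are the natural reading. What remains is that no metric, contrast or lock date is given, and that the Cox problem arises even with one reading fixed in advance.

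**Conclusion.** The point holds as a should-fix matter of limited reach. The rule is undefined, and chance triggers it often: 2-30% per binary covariate at prevalence 0.05-0.5 (points, pooled), 63% on a standardised difference (pooled) and 91% for any pair. The effect on the primary SDMT test is negligible with main effects and complete covariates.

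The main harm is in the secondary Cox models when events are near 10 and the reading admits a dozen or more covariates. There the hazard ratio is unstable and likelihood-ratio error is roughly 8-13% with independent covariates, or up to about 20% with a correlated mix, while Wald error stays near or below 6%. The loss of participants is conditional on listwise deletion and on missingness that the documents do not quantify.

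These sizes rest on assumed CVs, prevalences and correlations. The SAP text before section III was not available, so a definition there cannot be ruled out.

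**What to change.** 1. **Mixed models in section VIII.** Replace VIII.a with a closed list: MS subtype as randomised, age, sex and years of education, entered as baseline main effects. State that no covariate is added because of observed imbalance, and that a missing numeric baseline covariate is set to the overall baseline mean, so that nobody eligible under VIII.d is dropped.
2. **Cox models.** Do not apply the imbalance rule. Adjust for MS subtype only, or stratify by it, and keep the log-rank test as the unadjusted result. Insulin plus subtype is 2 parameters, or 5 events per parameter at 10 events; the four-covariate list would leave 10/5 = 2.
3. **Sensitivity analysis, mixed models only.** Define imbalance as a standardised difference above 0.1 for pooled insulin versus placebo, over the V.b.i list, with the selected set fixed before outcomes are seen by arm.

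The protocol's Aim 2 analysis names a different covariate set (including HOMA-IR, body composition and depression), so the SAP should say how the two relate.

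Cost: SAP wording only, since the closed-list variables are already planned for collection. The downside is that chance imbalances are then handled in a sensitivity analysis rather than in the primary model.

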PROTOCOL TITLE: INTRANASAL INSULIN FOR IMPROVING COGNITIVE FUNCTION IN MULTIPLE SCLEROSIS

DATE: November 20, 2020

VERSION: 2.4

SYNOPSIS

This will be a randomized, double-blind, placebo-controlled phase I/II pilot study. Participants will be randomized to intranasal insulin 10 international units (IU) twice a day, 20 IU twice a day, or placebo for 24 weeks. Insulin will be administered intranasally using the novel ViaNaseTM controlled particle dispersion system, allowing for direct delivery of the medication to the nasal epithelium, leading to maximal transport to the CNS (Kurve Technology, Lynnwood, WA).³⁴ Cognitive assessments will occur at baseline and throughout the 24-week trial, as well as for a period of 24 weeks after discontinuation of the intervention, to evaluate the impact of insulin on cognitive performance as well as the longevity of the treatment response. Biomarkers of cellular stress, neuronal injury, oxidative stress, inflammation, and energy metabolism will be assessed at baseline and at subsequent visits. Stored specimens will be acquired for more detailed future mechanistic studies if intranasal insulin does appear to be safe and effective.

INTRODUCTION

Cognitive impairment is common in and devastating to people with MS. MS is a common, chronic, central nervous system (CNS) disease characterized by inflammation, demyelination, and neurodegeneration. One of the most devastating symptoms of this disease is impaired cognitive function, which is common and present in over 60% of individuals with MS.¹⁻³ MS-related cognitive impairment is associated with lowered quality of life ⁴ and reduced functional capacity, including loss of employment,⁴⁻⁷ impaired social relationships,⁸ compromised driving safety,⁷ and poor adherence to treatment.⁹ Impaired cognitive functioning has been observed early in the disease, sometimes even before diagnosis,¹⁰ and cognitive function has been shown to decline longitudinally, both over the short- and long-term.¹¹⁻¹³ Several cognitive domains are impacted in people with MS, including attention, memory, executive functioning, and especially processing speed.^{2, 10, 14-18}

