Safety Since this medication was extremely well-tolerated in several published studies,³⁴⁻⁵⁰ we anticipate the same will be true for people with MS. In prior studies, there was no effect of intranasal insulin on serum glucose levels. However, we will monitor the first 15 participants for a period of 90 minutes after their first dose of the medication to evaluate serial finger stick blood glucose levels. If there is a clinically significant reduction in these levels, we will convene a Data Safety Monitoring Board (DSMB) meeting to adjust the protocol. We will also record and, when appropriate, report all patient-reported adverse events, as described below. Subjects and their caregivers will be required to keep an electronic diary of adverse events, which will be reviewed at each study visit. As mandated by the FDA, the Columbia Suicide Severity Rating Scale will be administered at each study visit.

Cognitive Assessments The MACFIMS battery includes the following: The Symbol Digit Modalities Test (SDMT) is commonly used in MS to assess processing speed.^{1, 52-54} The oral version of the test is recommended for MS since the written version may be confounded by upper extremity weakness.^{53, 55, 56} There are three alternate versions of this test with strong psychometric properties.³⁷ A 3.5-4 point raw score difference on the SDMT has been identified as clinically meaningful.^{6, 57} The Controlled Oral Word Association Test (COWAT) measures phonemic fluency.⁵⁸ The California Verbal Learning Test, Second Edition (CVLT-II) is a verbal learning and memory test.^{55, 59} The Brief Visuospatial Memory Test – Revised (BVMT-R) is a visual, nonverbal test of learning and memory.⁶⁰ The Rao-version of the Paced Auditory Serial Addition Test (PASAT) evaluates processing speed, working memory, and basic addition skills.⁵⁸ Visual-spatial abilities are assessed with the Judgement of Line Orientation Test (JLO).^{58, 61} The Delis-Kaplan Executive Function System (DKEFS) tests executive functioning, concept formation, and cognitive flexibility.

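### The 0–48 week analysis meant to assess a sustained effect names one INI-by-time coefficient spanning the week-24 treatment stop, and no between-arm off-treatment estimate

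*SAP*

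**What the plan says.** The protocol Synopsis sets 24 weeks of treatment, then 24 weeks of observation, with cognitive testing throughout "to evaluate the impact of insulin on cognitive performance as well as the longevity of the treatment response". The protocol section on additional outcomes gives detection of cognitive decline after stopping as a purpose of the follow-up. The Analytic Plan for Aim 2 says SDMT at each visit, and other MACFIMS outcomes at week 48, will be used to judge longevity.

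SAP VIII.c runs the models first on weeks 0, 6, 12 and 24, and then: "Secondary analyses will include weeks 36 and 48 (0, 6, 12, 24, 36, 48) to evaluate a potential sustained effect post cessation of treatment".

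The model for SDMT (VIII.g.i) is: "Change in the raw SDMT score over time will be assessed using a linear mixed effects model with unstructured covariance structure, random intercepts", with random slopes added if they improve fit. The quantity to be read from it is: "The term of interest will be the coefficient for the cross-product term between INI and time". The same term is repeated in VIII.h for the other cognitive tests, MSFC, FAMS, sleep and depression; the depression entry, for example, begins "Rate of change in total depression using a linear mixed effects model with unstructured covariance structure, random intercepts".

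On the shape of time, VIII.f says: "For mixed effects models, time will be considered as a linear variable in primary analyses". VIII.f.i adds: "Sensitivity analyses will evaluate potential non-linearity in changes over time using appropriate methods (e.g., quadratic terms for time or splines". No knot, contrast or separate form is given for the 0–48 week analysis. SAP V.c provides SDMT descriptive statistics and plots by arm, in one version through week 48.

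**The concern.** The question is what happens between the arms once treatment stops. The named coefficient is the average weekly divergence over the whole 48 weeks. Half of that span is on treatment, and nothing in the model changes at week 24. A positive slope can come from a gain that is kept, from slow divergence throughout, or from a difference that appears only off treatment. A null slope can mean no effect at any time, or a gain that was lost.

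At stake is the return on 24 weeks of follow-up. If the team sees that the slope does not answer the question, any knot or contrast added then would be chosen with the data in view.

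**Working it through.** **Inputs.** From the protocol's Sample Size and Power section: SDMT SD 9, a 6-point effect, 35 per arm. Pooled INI is therefore 70 against 35, the comparison that SAP VIII.b tests first. The correlation of 0.5 is stated there for a different outcome; using it for SDMT is my assumption. Compound symmetry is what a random-intercept model implies. I also tried serial correlation of 0.8 per 12 weeks. The profiles are illustrative and the data complete.

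**1. The plan's own figure.** 6 / (9·√(2/35)) = 6 / 2.151 = 2.789. Power = Φ(2.789 − 1.960) = 0.796, matching the stated 80%.

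**2. What the 0–48 slope estimates.** Under compound symmetry with an arm main effect, slope = Σ(t − t̄)d / Σ(t − t̄)², where d is the INI–placebo difference. For visits 0, 6, 12, 24, 36, 48, t̄ = 21, the deviations are −21, −15, −9, 3, 15, 27, and the sum of squares is 1710. SE = √[81·(1 − 0.5)·(1/70 + 1/35)/1710] = 0.0319.

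| Difference at 0, 6, 12, 24, 36, 48 | Calculation | Slope/week | True change, week 24 to 48 |
|---|---|---|---|
| 6 points, linear onset, kept (0, 1.5, 3, 6, 6, 6) | 220.5/1710 | 0.129 | 0 |
| Nothing on treatment, 6 after (0, 0, 0, 0, 3, 6) | 207/1710 | 0.121 | +6 |
| 3 points, linear onset, kept (0, 0.75, 1.5, 3, 3, 3) | 110.25/1710 | 0.064 | 0 |
| 6 points, linear onset, half lost (0, 1.5, 3, 6, 3, 3) | 94.5/1710 | 0.055 | −3 |
| 3 points, rapid onset, kept (0, 3, 3, 3, 3, 3) | 63/1710 | 0.037 | 0 |
| 6 points, rapid onset, half lost (0, 6, 6, 6, 3, 3) | 0/1710 | 0.000 | −3 |

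The first pair differs by 0.0079, or 0.25 SE. The second differs by 0.0092, or 0.29 SE, although the true off-treatment changes are 3 points apart. For scale, the protocol says: "A 3.5-4 point raw score difference on the SDMT has been identified as clinically meaningful". The rapid-onset pair differs by 0.037, or 1.16 SE.

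**3. Sensitivity.** MACFIMS, which contains the SDMT, is not scheduled at week 6. Without week 6, the first pair is 0.125 and 0.125. Also without week 36 (the COVID-19 schedule), it is 0.121 and 0.129. Under serial correlation it is 0.125 for both, the second pair is 0.0625 and 0.0615, and the rapid-onset pair is 0.0607 and 0.0579 (SE 0.0422).

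**4. A direct contrast.** SE of the week 24-to-48 change in difference = √[2·81·(1 − ρ)·(1/70 + 1/35)]. With ρ = 0.5 this is 1.86. Under serial correlation, ρ = 0.8² = 0.64 gives 1.58. Under compound symmetry the second pair gives 0 (95% CI −3.7 to 3.7) against −3 (−6.7 to 0.7), and the off-treatment-only profile gives +6 (2.3 to 9.7).

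**5. A spline with a week-24 knot.** For a rapid 6-point gain gone by week 36 (0, 6, 6, 6, 0, 0) under compound symmetry, the fitted week 24-to-48 change is −7.4 against a true −6. The fitted baseline difference is +2.65 and the fitted week-48 level is −1.2, so the model-based change from baseline at week 48 is −3.9 against a truth of 0. Under serial correlation that last figure is −0.3.

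**The case against.** The plan is not silent on persistence. VIII.c runs weeks 0–24 before 0–48, and the two slopes together are informative. The 0–24 slopes are 0.25 against 0 for the first pair and 0.125 against 0.25 for the second. For the same 6-point linear gain, kept against half lost, the 0–48 slopes themselves differ: 0.129 against 0.055, which is 2.3 SE. The VIII.f.i splines and V.c summaries would also let a reader see a pattern. All of this stands, but it is qualitative: none of it yields a between-arm off-treatment difference with an interval.

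Other analyses exist, but they do not fill the gap. The Cox and log-rank analyses of MSFC and FAMS concern time to an event. The Aim 2 paired t-tests are within person, and the Aim 2 between-group ANOVA and mixed model stop at week 24. VIII.b repeats the slope for dose pairs. VIII.f states linear time for primary analyses only, so its use for 0–48 weeks is inferred because no other form is given.

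The direct contrast is also imprecise: in the second pair, −3 does not exclude zero. The protocol itself does not expect conclusive evidence of efficacy. That limits the gain but does not make the slope the right quantity.

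A reader might infer that a benefit followed by loss would be reported as significant worsening. That is possible but not robust. The rapid-loss profile gives z = −2.3 with all visits under compound symmetry, −1.4 without week 6, and −0.1 under serial correlation.

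**Conclusion.** The point holds as a gap in specification. SAP sections III to IX (the earlier part was not available) name no between-arm estimate or test for the off-treatment period, and the 0–48 slope does not estimate retention or loss after week 24. This rests on the text; the numbers illustrate it. The near-equality of slopes needs the assumed onset and correlation, and rapid onset under compound symmetry weakens it.

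Two broader readings are not supported. One is that the plan can show nothing about persistence: the paired slopes, splines and summaries show it qualitatively. The other is that the main efficacy result is compromised: the 0–24 week primary analysis is unaffected. This is a secondary question, worth settling before the analysis because the follow-up exists to answer it.

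**What to change.** In SAP VIII.c, for the 0–48 week analysis, prespecify with 95% CIs:

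- the INI–placebo difference in change from baseline at week 48, and at week 36 where the outcome was obtained;
- the change in that difference from week 24 to week 48.

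Use categorical visit, which imposes no shape. A linear spline with a week-24 knot is acceptable for the second quantity, but its model-based change from baseline at week 48 can be biased after an abrupt change (step 5 of the working). Present both quantities as estimates.

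Add a sensitivity analysis limited to week-48 visits inside the ordinary window, because the protocol's COVID-19 schedule conditionally allows that visit up to 3 months late.

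The cost is SAP wording and a few more parameters; no new data are needed. Some power is lost if a linear 6-point gain is fully kept: under compound symmetry, z = 6/1.86 = 3.2 for the week-48 contrast against 0.129/0.0319 = 4.0 for the slope. Under serial correlation both are 3.0. If 30% of each arm lacks week 48, the SE of that contrast rises to about 1.86/√0.7 = 2.2 points under compound symmetry.
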